9.3.1.3 Safety Assessment Methods

At each visit, the Investigator or a delegate will perform a directed physical examination, if indicated, based on interim history and will ask the subject or subject’s parent/guardian about any solicited reactions and unsolicited AEs recorded in the diary card, as well as about any other AEs that may have occurred since the previous visit. All relevant data will be transcribed into the CRB according to the instructions provided by the Sponsor.

9.3.1.3.1 Immediate Post-vaccination Observation Period

Subjects will be kept under observation for 20 minutes after each vaccination to ensure their safety. The post-vaccination observation should be documented in the source document. Any AE that occurs during this period will be noted on the source document and recorded in the CRB, as follows:

- Unsolicited systemic AEs will be recorded as immediate AEs in the CRB (presence marked as “yes” and details collected).
- Solicited and unsolicited injection site reactions and solicited systemic reactions will be recorded in the CRB in the same way as any reactions starting on the day of vaccination.
- SAEs will be recorded in the CRB and reported to the Sponsor in the same way as any other SAEs, according to the procedures described in [Section 10](#).

9.3.1.3.2 Reactogenicity (Solicited Reactions From Day 0 Through Day 7 After Each Vaccination)

After each vaccination, the subject or the subject’s parent/guardian will be provided with a diary card, a digital thermometer, and a flexible ruler, and will be instructed how to use them. The following items will be recorded by the subject or the subject’s parent/guardian in the diary card on the day of vaccination and for the next 7 days (i.e., Day 0 through Day 7) until resolution:

- Daily temperature, with the route by which it was taken
- Daily measurement or intensity grade of all other solicited injection site and systemic reactions
- Action taken for each event (e.g., medication)

The action(s) taken by the subject or subject’s parent/guardian to treat and/or manage any **solicited reactions** will be classified in the CRB using the following list (all applicable items should be checked):

- None
- Medication
- Health care provider contact
- Hospitalized
- Discontinuation of study vaccination

The subject or subject’s parent/guardian will be contacted by telephone 8 days after each vaccination to remind them to record all safety information in the diary card.

If the timing of the telephone call should fall on a weekend or a holiday, the call should be made on the next business day. If contact is not made on the designated day, study staff will continue calling until contact is made. Every telephone attempt and its outcome will be documented in the source document.

[Table 9.1](#), [Table 9.2](#), [Table 9.3](#), [Table 9.4](#), and [Table 9.5](#) present the injection site reactions and systemic reactions that are prelisted in the diary cards and CRB, together with the intensity scales.

Table 9.1: Solicited Injection Site Reactions: Terminology, Definitions, and Intensity Scales (Subjects 6 to < 36 Months of Age)

CRB term (MedDRA lowest level term [LLT])	Injection site tenderness	Injection site erythema	Injection site swelling
Data analysis term (MedDRA preferred term [PT])	Injection site pain	Injection site erythema	Injection site swelling
Diary card term	Tenderness	Redness	Swelling
Definition	Pain when the injection site is touched or injected limb mobilized	Presence of a redness including the approximate point of needle entry	Swelling at or near the injection site Swelling or edema is caused by a fluid infiltration in tissue or cavity and, depending on the space available for the fluid to disperse, swelling may be either soft (typically) or firm (less typical) to touch and thus can be best described by looking at the size of the swelling
Intensity scale^a	Grade 1: Minor reaction when injection site is touched Grade 2: Cries or protests when injection site is touched Grade 3: Cries when injected limb is mobilized, or the movement of the injected limb is reduced	Grade 1: > 0 to < 25 mm Grade 2: ≥ 25 to < 50 mm Grade 3: ≥ 50 mm	Grade 1: > 0 to < 25 mm Grade 2: ≥ 25 to < 50 mm Grade 3: ≥ 50 mm

^a For the subjective reaction of tenderness, parents/guardians will record the intensity level (Grade 1, 2, or 3) in the diary card. For the measurable reactions of redness and swelling, they will record just the size of the reaction, and the classification as Grade 1, 2, or 3 will be assigned at the time of the statistical analysis.

Table 9.2: Solicited Injection Site Reactions: Terminology, Definitions, and Intensity Scales (Subjects 3 to < 9 Years of Age)

CRB term (MedDRA lowest level term [LLT])	Injection site pain	Injection site erythema	Injection site swelling
Data analysis term (MedDRA preferred term [PT])	Injection site pain	Injection site erythema	Injection site swelling
Diary card term	Pain	Redness	Swelling
Definition	Pain either present spontaneously or when the injection site is touched or injected limb is mobilized	Presence of a redness including the approximate point of needle entry	Swelling at or near the injection site Swelling or edema is caused by a fluid infiltration in tissue or cavity and, depending on the space available for the fluid to disperse, swelling may be either soft (typically) or firm (less typical) to touch and thus can be best described by looking at the size of the swelling
Intensity scale^a	Grade 1: Easily tolerated Grade 2: Sufficiently discomforting to interfere with normal behavior or activities Grade 3: Incapacitating, unable to perform usual activities	Grade 1: > 0 to < 25 mm Grade 2: ≥ 25 to < 50 mm Grade 3: ≥ 50 mm	Grade 1: > 0 to < 25 mm Grade 2: ≥ 25 to < 50 mm Grade 3: ≥ 50 mm

^a For the subjective reaction of pain, subjects or subjects' parents/guardians will record the intensity level (Grade 1, 2, or 3) in the diary card. For the measurable reactions of redness and swelling, they will record just the size of the reaction, and the classification as Grade 1, 2, or 3 will be assigned at the time of the statistical analysis.

Table 9.3: Solicited Injection Site Reactions: Terminology, Definitions, and Intensity Scales (Subjects 18 Years of Age and Older)

CRB term (MedDRA lowest level term [LLT])	Injection site pain	Injection site erythema	Injection site swelling
Data analysis term (MedDRA preferred term [PT])	Injection site pain	Injection site erythema	Injection site swelling
Diary card term	Pain	Redness	Swelling
Definition	Pain either present spontaneously or when the injection site is touched or injected limb is mobilized	Presence of a redness including the approximate point of needle entry	Swelling at or near the injection site Swelling or edema is caused by a fluid infiltration in tissue or cavity and, depending on the space available for the fluid to disperse, swelling may be either soft (typically) or firm (less typical) to touch and thus can be best described by looking at the size of the swelling

Intensity scale^a
	
Grade 1: A type of adverse event that is usually transient and may require only minimal treatment or therapeutic intervention. The event does not generally interfere with usual activities of daily living.
 
Grade 2: A type of adverse event that is usually alleviated with additional therapeutic intervention. The event interferes with usual activities of daily living, causing discomfort but poses no significant or permanent risk of harm to the research participant.
 
Grade 3: A type of adverse event that interrupts usual activities of daily living, or significantly affects clinical status, or may require intensive therapeutic intervention.
	
Grade 1: ≥ 25 to ≤ 50 mm Grade 2: ≥ 51 to ≤ 100 mm Grade 3: > 100 mm
	
Grade 1: ≥ 25 to ≤ 50 mm Grade 2: ≥ 51 to ≤ 100 mm Grade 3: > 100 mm

---	--	---	---

^a For the subjective reaction of pain, subjects will record the intensity level (Grade 1, 2, or 3) in the diary card. For the measurable reactions of redness and swelling, they will record just the size of the reaction, and the classification as Grade 1, 2, or 3 will be assigned at the time of the statistical analysis

Table 9.4: Solicited Systemic Reactions: Terminology, Definitions, and Intensity Scales (Subjects 6 to < 36 Months of Age)

CRB term (MedDRA lowest level term [LLT])	Fever	Vomiting	Crying abnormal	Drowsiness	Appetite lost	Irritability
Data analysis term (MedDRA preferred term [PT])	Pyrexia	Vomiting	Crying	Somnolence	Decreased appetite	Irritability
Diary card term	Temperature	Vomiting	Abnormal crying	Drowsiness	Loss of appetite	Irritability
Definition	Elevation of temperature to $\geq 38.0^{\circ}\text{C}$ ($\geq 100.4^{\circ}\text{F}$)	Vomiting does not include spitting up	Inconsolable crying without a determined reason	Reduced interest in surroundings, or increased sleeping	See intensity scale	An excessive response to stimuli: increased fussiness, whining, and fretfulness despite attempts to comfort the infant and despite caregiver responses that would normally be soothing
Intensity scale^a	Grade 1: $\geq 38.0^{\circ}\text{C}$ to $\leq 38.5^{\circ}\text{C}$ or $\geq 100.4^{\circ}\text{F}$ to $\leq 101.3^{\circ}\text{F}$ Grade 2: $> 38.5^{\circ}\text{C}$ to $\leq 39.5^{\circ}\text{C}$ or $> 101.3^{\circ}\text{F}$ to $\leq 103.1^{\circ}\text{F}$ Grade 3: $> 39.5^{\circ}\text{C}$ or $> 103.1^{\circ}\text{F}$	Grade 1: 1 episode per 24 hours Grade 2: 2–5 episodes per 24 hours Grade 3: ≥ 6 episodes per 24 hours or requiring parenteral hydration	Grade 1: < 1 hour Grade 2: 1–3 hours Grade 3: > 3 hours	Grade 1: Sleepier than usual or less interested in surroundings Grade 2: Not interested in surroundings or did not wake up for a feed/meal Grade 3: Sleeping most of the time or difficult to wake up	Grade 1: Eating less than normal Grade 2: Missed 1 or 2 feeds/meals completely Grade 3: Refuses ≥ 3 feeds/meals or refuses most feeds/meals	Grade 1: Easily consolable Grade 2: Requiring increased attention Grade 3: Inconsolable

^a For all reactions but fever, parents/guardians will record the intensity level (Grade 1, 2, or 3) in the diary card. For fever, they will record the body temperature, and the classification as Grade 1, 2, or 3 will be assigned at the time of the statistical analysis based on the unit used to measure the temperature and the intensity scale.

Table 9.5: Solicited Systemic Reactions: Terminology, Definitions, and Intensity Scales (Subjects 3 to < 9 Years of Age and 18 Years of Age and Older)

CRB term (MedDRA lowest level term [LLT])	Fever	Headache	Malaise	Myalgia
Data analysis term (MedDRA preferred term [PT])	Pyrexia	Headache	Malaise	Myalgia
Diary card term	Temperature	Headache	Feeling unwell	Muscle aches and pains
Definition	Elevation of temperature to $\geq 38.0^{\circ}\text{C}$ ($\geq 100.4^{\circ}\text{F}$)	Pain or discomfort in the head or scalp. Does not include migraine.	General ill feeling. Malaise is a generalized feeling of discomfort, illness, or lack of well-being that can be associated with a disease state. It can be accompanied by a sensation of exhaustion or inadequate energy to accomplish usual activities.	Muscle aches and pains are common and can involve more than one muscle at the same time. Muscle pain can also involve the soft tissues that surround muscles. These structures, which are often referred to as connective tissues, include ligaments, tendons, and fascia (thick bands of tendons). Does not apply to muscle pain at the injection site which should be reported as injection site pain.
Intensity scale ^a	Grade 1: $\geq 38.0^{\circ}\text{C}$ to $\leq 38.4^{\circ}\text{C}$, or $\geq 100.4^{\circ}\text{F}$ to $\leq 101.1^{\circ}\text{F}$	Grade 1: A type of adverse event that is usually transient and may require only minimal treatment or therapeutic intervention. The event does not generally interfere with usual activities of daily living.	Grade 1: A type of adverse event that is usually transient and may require only minimal treatment or therapeutic intervention. The event does not generally interfere with usual activities of daily living.	Grade 1: A type of adverse event that is usually transient and may require only minimal treatment or therapeutic intervention. The event does not generally interfere with usual activities of daily living.

	
Grade 2: $\geq 38.5^{\circ}\text{C}$ to $\leq 38.9^{\circ}\text{C}$, or $\geq 101.2^{\circ}\text{F}$ to $\leq 102.0^{\circ}\text{F}$
 
Grade 3: $\geq 39.0^{\circ}\text{C}$ or $\geq 102.1^{\circ}\text{F}$
	
Grade 2: A type of adverse event that is usually alleviated with additional therapeutic intervention. The event interferes with usual activities of daily living, causing discomfort but poses no significant or permanent risk of harm to the research participant.
 
Grade 3: A type of adverse event that interrupts usual activities of daily living, or significantly affects clinical status, or may require intensive therapeutic intervention.
	
Grade 2: A type of adverse event that is usually alleviated with additional therapeutic intervention. The event interferes with usual activities of daily living, causing discomfort but poses no significant or permanent risk of harm to the research participant.
 
Grade 3: A type of adverse event that interrupts usual activities of daily living, or significantly affects clinical status, or may require intensive therapeutic intervention.
	
Grade 2: A type of adverse event that is usually alleviated with additional therapeutic intervention. The event interferes with usual activities of daily living, causing discomfort but poses no significant or permanent risk of harm to the research participant.
 
Grade 3: A type of adverse event that interrupts usual activities of daily living, or significantly affects clinical status, or may require intensive therapeutic intervention.

--	---	--	--	--

^a For all reactions but fever, subjects or subjects’ parents/guardians will record the intensity level (Grade 1, 2, or 3) in the diary card. For fever, they will record the body temperature, and the classification as Grade 1, 2, or 3 will be assigned at the time of the statistical analysis based on the unit used to measure the temperature and the intensity scale.

Important notes for the accurate assessment of temperature:

Subjects or subjects’ parents/guardians are to measure body temperature once per day, preferably always at the same time. The optimal time for measurement is the evening, when body temperature is the highest. Temperature is also to be measured at the time of any apparent fever. The observed daily temperature and the route of measurement are to be recorded in the diary card, and the highest temperature will be recorded by the site in the CRB. The preferred route for this study is rectal for subjects 6 to < 36 months of age, and oral for subjects 3 to < 9 years of age and ≥ 18 years of age. The axillary route may be used when a rectal or oral temperature cannot be obtained. Pre-vaccination temperature is also to be systematically collected by the Investigator on the source document. Tympanic thermometers must not be used.

9.3.1.3.3 Unsolicited Adverse Events

In addition to recording solicited reactions, subjects or subjects’ parents/guardians will be instructed to record any other medical events that may occur from Visit 1 through Visit 2 (Diary Card 1) for all subjects and from Visit 2 through Visit 3 (Diary Card 2) for subjects receiving 2 doses of study vaccine. Space will be provided in the diary card for this purpose.

Information on SAEs will be collected and assessed throughout the study, from Visit 1 through Visit 2 for subjects receiving 1 dose of study vaccine, and from Visit 1 through Visit 3 for subjects receiving 2 doses of study vaccine.

Any SAE occurring at any time during the study will be reported by the Investigator in the CRB according to the completion instructions provided by the Sponsor; this includes checking the “Serious” box on the AE CRF and completing the appropriate Death/Safety Complementary Information CRFs. All information concerning the SAE is to be reported either as part of the initial reporting or during follow-up reporting if relevant information became available later (e.g., outcome, medical history, results of investigations, copy of hospitalization reports). See [Section 10](#) for further details on SAE reporting.

For each unsolicited AE (whether serious or non-serious), the following information is to be recorded:

- Start and stop dates^a
- Intensity of the event:

For measurable unsolicited AEs that are part of the list of solicited reactions, the size of the AE as well as the temperature for fever will be collected and analyzed based on the corresponding scale used for solicited reactions (see [Table 9.1](#), [Table 9.2](#), [Table 9.3](#), [Table 9.4](#), and [Table 9.5](#)).

^a The stop date of all related AEs will be actively solicited. For other events, the Investigator will provide the stop date when it becomes available. AEs for which no stop date was obtained during the course of the study will be considered as ongoing at the end of the study.

All other unsolicited AEs will be classified according to the following intensity scale:

- Grade 1: A type of AE that is usually transient and may require only minimal treatment or therapeutic intervention. The event does not generally interfere with usual activities of daily living.
 - Grade 2: A type of AE that is usually alleviated with additional therapeutic intervention. The event interferes with usual activities of daily living, causing discomfort but poses no significant or permanent risk of harm to the research participant.
 - Grade 3: A type of AE that interrupts usual activities of daily living, or significantly affects clinical status, or may require intensive therapeutic intervention.
- Whether the AE was related to the investigational product (for unsolicited systemic AEs)
The Investigator will assess the causal relationship between the AE and the investigational product as either “Not related” or “Related”, as described in [Section 9.3.1.3.5](#).
 - Action taken for each AE (e.g., medication)
The action(s) taken by the subject or subject’s parent(s)/guardian(s) to treat and/or manage any unsolicited AEs will be classified in the CRB using the following list (all applicable items should be checked):
 - None
 - Medication
 - Health care provider contact
 - Hospitalized
 - Discontinuation of study vaccination
 - Whether the AE was serious
For each SAE, the Investigator will complete all seriousness criteria that apply (outcome, elapsed time, and relationship to study procedures)
 - Whether the AE caused study discontinuation

9.3.1.3.4 Adverse Events of Special Interest

Adverse events of special interest will be captured as SAEs. These include new onset of GBS, encephalitis/myelitis (including transverse myelitis), neuritis (including Bell’s palsy, optic neuritis, and brachial neuritis), thrombocytopenia, vasculitis, convulsions (including febrile convulsions [children only]), and anaphylaxis or other hypersensitivity/allergic reactions from Visit 1 through Visit 2 for subjects receiving 1 dose of vaccine, or from Visit 1 through Visit 3 for subjects receiving 2 doses of vaccine.

9.3.1.3.5 Assessment of Causality

The Investigator will assess the *causal relationship* between each unsolicited systemic AE and the product administered as either *not related* or *related*, based on the following definitions:

Not related – The AE is clearly/most probably caused by other etiologies such as an underlying condition, therapeutic intervention, or concomitant therapy; or the delay between vaccination and the onset of the AE is incompatible with a causal relationship; or the AE started before the first vaccination (screening phase, if applicable)

Related – There is a “reasonable possibility” that the AE was caused by the product administered, meaning that there is evidence or arguments to suggest a causal relationship

Note: By convention, all AEs reported at the injection site (whether solicited or unsolicited) and all solicited systemic AEs are considered to be related to the administered product and, therefore, are referred to as reactions and do not require the Investigator’s opinion on relatedness.

Adverse events likely to be related to the product, whether serious or not, that persist at the end of the study will be followed up by the Investigator until their complete disappearance or the stabilization of the subject’s condition. The Investigator will inform the Sponsor of the date of final disappearance of the event or the date of “chronicity” establishment.

9.3.2 Immunogenicity

The observational immunogenicity objective is presented in [Section 2.1.2](#).

9.3.2.1 Immunogenicity Endpoints

Immunogenicity will be evaluated in all subjects by analyzing sera collected prior to vaccination on Day 0 (Visit 1) and after final vaccination (28 [window, 28–35] days post-final vaccination for subjects 6 months to < 9 years of age [Visit 2 for subjects receiving 1 dose; Visit 3 for subjects receiving 2 doses]; or 21 [window, 21–28] days post-vaccination for subjects \geq 18 years of age) using the HAI assay technique.

For each influenza vaccine strain (i.e., 3 strains for Fluzone High-Dose vaccine [a trivalent vaccine] and 4 strains for Fluzone Quadrivalent vaccine and Flublok Quadrivalent vaccine), HAI assay titers at pre-vaccination (Day 0) and after the final vaccination will be determined in duplicate.

The derived endpoints^a are:

- Geometric means of HAI assay titers at pre-vaccination and post-final vaccination
- Ratios of post-final vaccination titers divided by pre-vaccination titers
- Seroprotection: a titer \geq 40 (1/dilution [dil]) at pre-vaccination and at post-final vaccination
- Seroconversion: either a pre-vaccination titer $<$ 10 (1/dil) and a post-final vaccination titer \geq 40 (1/dil), or a pre-vaccination titer \geq 10 (1/dil) and a \geq 4-fold increase in post-final vaccination titer

- ^a Post-final vaccination in each of the derived endpoints is defined as 28 (window, 28–35) days post-final vaccination for subjects 6 months to < 9 years of age, and 21 (window, 21–28) days post-vaccination for subjects \geq 18 years of age

9.3.2.2 Immunogenicity Assessment Methods

Anti-influenza antibodies will be measured by HAI assay performed by Sanofi Pasteur’s GCI department or an external testing laboratory under GCI’s supervision. Serum samples and quality control sera (sheep and/or human sera) will be incubated with Sigma Type III NA to eliminate non-specific inhibitors. Adsorption of spontaneous anti-species agglutinins will be performed by incubating the serum samples and quality control sera with a red blood cell (RBC) suspension. Following this, the mixtures will be centrifuged and the supernatants containing the treated sera will be collected for testing. Ten 2-fold dilutions (starting at 1/10) of the treated serum samples and quality control sera will be incubated with a previously titrated influenza virus at a concentration of 4 hemagglutination unit/25 μ L. Influenza virus will not be added to the serum control wells containing only serum and RBCs. The mixture will be incubated and a RBC suspension will be added. Following incubation, the results will be read. The endpoint of the assay is the highest serum dilution in which complete inhibition of hemagglutination occurred. Each serum sample will be titrated in independent duplicates, and the 2 values, which do not differ by more than one 2-fold dilution, will be reported. The geometric mean titer between the 2 values will be calculated after the release of the data to the Clinical Data Management (CDM) platform. The lower limit of quantification (LLOQ) for HAI is set at 10, the lowest serum dilution used in the assay (i.e., 1/10). Titers below this level are reported as < 10. If the highest/last serum dilution used in the assay exhibits complete inhibition of hemagglutination, the serum antibody titer will be reported as \geq 10240 (1/dil).

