12.3.2 Immunogenicity

For the computations, LLOQ and upper limit of quantification (ULOQ) will be managed as follows:

- If a titer is $< \text{LLOQ}$, then $\text{LLOQ}/2$ will be used
- If a titer is $\geq \text{LLOQ}$ and $< \text{ULOQ}$, then the titer itself will be used

- If a titer is \geq ULOQ, then ULOQ will be used

Missing data will not be imputed. No search for outliers will be performed.

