4.4.2 Immunogenicity

4.4.2.1 Computed Values for Analysis

To appropriately manage extreme values ($< \text{LLOQ}$ [lower limit of quantification] and $\geq \text{ULOQ}$ [upper limit of quantification]) for analysis purposes, the following computational rule will be applied to the values provided in the clinical database for each BL (blood sample) drawn:

In order to appropriately manage replicate values for analysis purposes, the individual GM of all values will be computed for each BL after managing extreme values as described:

- If a value is $< \text{LLOQ}$, then the computed value $\text{LLOQ}/2$ will be used
- If a value is between $\geq \text{LLOQ}$ and $< \text{ULOQ}$, then the value will be used
- If a value is $\geq \text{ULOQ}$, then the value ULOQ will be used

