4.4.2.3 Fold-rise

The derived endpoint fold-rise is driven by both baseline and post-baseline computed values and is computed as follows. Generally, for extreme values, this algorithm minimizes the numerator and maximizes the denominator.

- If the baseline computed value is < LLOQ and the post-baseline computed value is < LLOQ then the fold-rise is 1
- If the baseline computed value is \geq LLOQ and the post-baseline computed value is \geq LLOQ then the fold-rise is post-baseline computed value / baseline computed value
- If the baseline computed value is \geq LLOQ and the post-baseline computed value is < LLOQ then the fold-rise is (LLOQ/2)/baseline computed value
- If the baseline computed value is < LLOQ and the post-baseline computed value is \geq LLOQ then the fold-rise is post-baseline computed value / LLOQ

Note: If baseline or post-baseline is missing, then fold-rise is missing.

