4.4.4.3 Duration of the Study

The duration of the study is computed in days as follows:

Maximum of all subjects (date of last visit, date of termination form) - minimum for all subjects (date of Visit 1) + 1.

5 Statistical Methods and Determination of Sample Size

The statistical analyses will be performed under the responsibility of the Sponsor’s Biostatistics platform using SAS® Version 9.4 software or later.

The results of the statistical analysis will be available in the final clinical study report (CSR).

For descriptive purposes, the following statistics will be presented:

Table 5.1: Descriptive statistics produced

Baseline characteristics and follow-up description	Categorical data	Number of subjects. Percentage of subjects.
	Continuous data	Mean, standard deviation (SD), quartiles, minimum, and maximum.
Clinical safety results	Categorical data	Solicited: Number and percentage (95% CIs) of subjects. Unsolicited: Number and percentage (95% CIs) of subjects, and number of events.
Immunogenicity results	Categorical data (seroprotection, seroconversion, cutoff)	Number and percentage (95% CIs) of subjects.
	Continuous data (titer / data†)	Log10: Mean and standard deviation. Anti-Log10 (work on Log10 distribution, and anti-Log10 applied): Geometric mean (GM), 95% CI of the GM, quartiles, minimum, and maximum. Graphical representation by a reverse cumulative distribution curve (RCDC).

The confidence interval (CI) for the single proportion will be calculated using the exact binomial method (Clopper-Pearson method, quoted by Newcombe (8), i.e., using the inverse of the beta integral with SAS®).

For immunogenicity results, assuming that Log_{10} transformation of the titers/data follows a normal distribution, at first, the mean and the 95% CI will be calculated on Log_{10} (titers/data) using the usual calculation for normal distribution (using Student's t distribution with n-1 degree of freedom), then antilog transformations will be applied to the results of calculations, in order to provide geometric means and their 95% CI.

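### The HAI dilution series in Protocol 9.3.2.2 ends at 1/5120 but its ceiling is reported as ≥10240, and neither document gives the ULOQ a number

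*Protocol*

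**What the plan says.** Protocol 9.3.2.2 (Immunogenicity Assessment Methods) fixes four things about the HAI assay:

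- The series: "Ten 2-fold dilutions (starting at 1/10) of the treated serum samples".
- The titer: "The endpoint of the assay is the highest serum dilution in which complete inhibition of hemagglutination occurred".
- The lower limit: the LLOQ is 10, which the section identifies as the lowest dilution used.
- The upper reporting rule: "If the highest/last serum dilution used in the assay exhibits complete inhibition of hemagglutination, the serum antibody titer will be reported as" ≥10240 (1/dil).

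The analysis rules then refer to a ULOQ. Protocol 12.3.2 says that for a titer at or above it "then ULOQ will be used", and SAP 4.4.2.1 says "then the value ULOQ will be used", applied before the geometric mean of the duplicates is taken. Neither section gives a number. SAP 5.3.2 points back to 4.4.2.1. SAP 4.4.2.3 states of the fold-rise: "Generally, for extreme values, this algorithm minimizes the numerator and maximizes the denominator". Its four cases mention only the LLOQ.

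**The concern.** Within one section, the number of dilutions and the ceiling cannot both be right under the section's own definition of the titer. They differ by a factor of two.

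The ULOQ is the value that the analysis substitutes for every ceiling result. The only candidate for it in either document is 10240, which is the disputed figure. If the laboratory runs ten dilutions and the programmer uses 10240, ceiling sera enter these outputs at twice the supported bound:

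- the geometric mean titer and the titer ratio;
- the reverse cumulative distribution curve;
- the statistics that SAP Section 5, Table 5.1 lists as "Geometric mean (GM), 95% CI of the GM, quartiles, minimum, and maximum".

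Such coding would also inflate the numerator of the fold-rise, against the principle stated in SAP 4.4.2.3. Since the true titer is right-censored, a 4-fold rise that appears only because of the doubling has not been demonstrated; it has not been shown false either.

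**Working it through.** **Inputs.** First dilution 10, factor 2, ten dilutions, ceiling ≥10240, and duplicates agreeing within one 2-fold dilution (all Protocol 9.3.2.2). Planned group sizes are 30 (Groups 1 and 2) and 60 (Groups 3 to 5) (Protocol 12.5). The share of sera at the ceiling is not given, so it is left as *f*.

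**The plan's figure.** The last dilution is first × 2^(number − 1).

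- Ten dilutions: 10, 20, 40, 80, 160, 320, 640, 1280, 2560, 5120. The last is 10 × 2^9 = 5120, so 10240 is not reproduced.
- Eleven dilutions: 10 × 2^10 = 10240. This reproduces the ceiling but not the count.
- Ten dilutions starting at 1/20: 20 × 2^9 = 10240. This contradicts the 1/10 start and the LLOQ of 10.
- Ten dilutions with the next, untested step reported: 10240. This contradicts the definition of the titer.

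**A consequence of taking both figures literally.** With ten wells and the last coded 10240, no single titration can return 5120. Duplicates in wells 9 and 10 would be coded 2560 and 10240, an apparent 4-fold gap for a one-step difference. Their geometric mean would be √(2560 × 10240) = 5120 instead of √(2560 × 5120) = 3620.

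**Effect on the geometric mean titer, if ten dilutions are run and ULOQ = 10240.** Doubling the value of a share *f* of sera multiplies the GMT by 2^f. A serum with only one duplicate at the ceiling counts half. The titer ratio is multiplied by 2^(f_post − f_pre).

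| Sera with both duplicates at the ceiling | n = 60 | n = 30 |
|---|---|---|
| 1 | 2^(1/60) = 1.0116 (+1.2%) | 2^(1/30) = 1.0234 (+2.3%) |
| 3 | 2^(3/60) = 1.0353 (+3.5%) | 2^(3/30) = 1.0718 (+7.2%) |

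One such serum is enough to make the tabulated maximum read 10240 instead of 5120.

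**Effect on seroconversion, same condition.** All pre- and post-vaccination duplicate pairs in the same or adjacent dilutions were compared with the last dilution valued at 5120 and at 10240. The 4-fold status differs in exactly three patterns:

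| Pre duplicates (GM) | Post duplicates | Fold, last = 5120 | Fold, last = 10240 |
|---|---|---|---|
| 1280, 1280 (1280) | 2560, last | 3620/1280 = 2.83 | 5120/1280 = 4.0 |
| 1280, 2560 (1810) | last, last | 5120/1810 = 2.83 | 10240/1810 = 5.66 |
| 2560, 2560 (2560) | last, last | 5120/2560 = 2.0 | 10240/2560 = 4.0 |

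Each such subject moves the rate by 1/60 = 1.7 points or 1/30 = 3.3 points. Seroprotection, with its cut-off of 40, does not change.

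**The case against.** The strongest objection is that the phrase can be read as ten doublings after 1/10, which gives 10240 exactly. The duplicate rule in the same section does use a 2-fold dilution to mean a step. That makes a slip in the count plausible, but it does not reconcile the text. The dilutions are the items incubated with virus, and the section names 1/10 as the lowest of them, so 1/10 is one of the ten.

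A second objection is that the section also holds the only number for the LLOQ, that SAP 4.3 refers to Protocol 9.3, and that a database value of ≥10240 would in practice supply the ULOQ. That is a fair account of what a programmer would probably do. It also means that the disputed figure would be used unexamined.

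Three further points stand:

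- The size is hypothetical, because nothing in the documents says how many sera reach the ceiling. The seroconversion changes need baseline titers of 1280 to 2560, which is 32 to 64 times the seroprotection cut-off.
- The count of three patterns assumes that duplicate agreement is judged by wells. If it is judged on coded values, the pair 2560 and 10240 fails the rule and two patterns remain.
- The study tests no hypothesis and has no acceptance criterion, so no formal conclusion turns on this.

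**Conclusion.** The concern holds. As written, Protocol 9.3.2.2 is inconsistent by exactly one 2-fold step, and nothing in Protocol 12.3.2 or the SAP resolves it. Whether the count or the ceiling is wrong cannot be settled from the documents.

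The effect on results is conditional on ten dilutions being run and the ULOQ being taken as 10240. It is small unless several sera in a group reach the ceiling. The percentages also assume that the planned 30 or 60 subjects all contribute a result. If eleven dilutions are run, or if 5120 is used as the ULOQ, no titer is overstated. The point should still be corrected, because the substitution rule for ceiling results cannot be applied from the documents without choosing a number.

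**What to change.** Ask the laboratory (the sponsor's own, or the external one that Protocol 9.3.2.2 allows) which dilution series is run. Then make one of two changes in that section:

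- if ten dilutions are run, change the ceiling from ≥10240 to ≥5120;
- if the series runs to 1/10240, change the count from ten to eleven.

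State the matching numeric ULOQ in Protocol 12.3.2 and SAP 4.4.2.1.

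The cost is one corrected figure in the protocol and one number added to each document, with no extra data. If the protocol change is classed as administrative, Protocol 5.4 requires that the IRB(s) and regulatory authorities be notified, but not IRB approval.
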